### **8.3.3.2.4 Proportion of Patients who Achieved TI for $\geq 20$ consecutive Weeks (140 consecutive Days)**

The proportion of patients who achieved TI for  $\geq 20$  Weeks (140 Days) will be summarized using the FAS Population and will be compared between the two treatment groups using the Cochran-Mantel-Haenszel (CMH) chi-square test, controlling for stratification factors.

Two-sided 95% confidence interval (CI) of the odds ratio will also be presented.

The 95% CI of the response rate will be presented by treatment group based on the exact method of Clopper-Pearson.

### **8.3.3.2.5 Mean Change from Baseline in EQ-5D-5L assessment**

The mean change from Baseline in EQ-5D-5L assessment will be summarized and analyzed using the FAS Population. A mixed model repeated measures (MMRM) analysis of covariance model (ANCOVA) model, controlling for stratification factors and baseline value of the corresponding parameter, will be used to assess treatment difference.

### **8.3.3.2.6 Mean Change from Baseline in Functional Subscale of PROMIS**

The mean change from Baseline in Functional Subscale of PROMIS will be summarized and analyzed using the FAS Population. A MMRM-ANCOVA model, controlling for stratification factors and baseline value of the corresponding parameter, will be used to assess treatment difference.

### **8.3.3.2.7 Mean Change from Baseline in Vitality Subscale of PROMIS**

The mean change from Baseline in Vitality Subscale of PROMIS will be summarized and analyzed using the FAS Population. A MMRM-ANCOVA model, controlling for stratification factors and baseline value of the corresponding parameter, will be used to assess treatment difference.

### **8.3.3.3 Analysis of Exploratory Efficacy Endpoints**

The additional efficacy analyses will use the FAS Population.

Additional efficacy analyses of continuous endpoints will use an MMRM/ANCOVA model using baseline value and other stratification factors as covariates.

Additional analyses of proportions will use the CMH model adjusting for stratification factors. Odds ratio and its associated 95% CI will be computed to compare between the roxadustat group and placebo. A two-sided 95% CI of the proportion based on the exact method of Clopper-Pearson will be computed for each treatment group.

Additional efficacy analyses of time-to-event endpoints will use the Cox Proportional Hazards model adjusting for stratification factors. Median time to event and associated 95% CI will be estimated using Kaplan-Meier method.

### **8.3.4 Patient Enrollment and Disposition**

Patient enrollment and disposition will be presented for all enrolled. The total number and percent of patients who completed or discontinued, and reasons for early discontinuation, will be summarized by dose cohort or treatment group using the FAS Population.

### **8.3.5 Demographics and Baseline Characteristics**

Demographic data and other patient characteristics as well as baseline disease characteristics will be summarized descriptively using the FAS and the Safety Populations.

### **8.3.6 Summary of Safety Data**

Summary of safety data will be based on the Safety Population. Safety parameters include adverse events, N (%) patients progressing to AML, laboratory parameters, vital signs, ECG parameters, prior and concomitant medication use. For each safety parameter, the last assessment made prior to the first dose of study treatment will be used as the baseline, unless otherwise specified. In general, safety data will be summarized descriptively; no inferential statistical procedures will be applied.

Adverse events will be coded using Medical Dictionary for Regulatory Activities (MedDRA). A treatment emergent adverse event (TEAE) is defined as any new or worsening of an existing condition occurred after the first dose of the study medication and within 28 days after the last dose of study medication. TEAEs will be tabulated to examine their frequency, severity, organ systems affected and relationship to study treatment. Deaths, SAEs, AEs leading to study or treatment discontinuation, and AEs of special interest will be listed or tabulated separately.

Laboratory tests, vital sign measurements, ECG parameters, as well as the changes from baseline will be summarized descriptively by assessment time point. Clinically significant changes from baseline in these safety parameters will be identified. Shift tables will summarize changes for selected laboratory measures.

Medications used prior to and during the study will be coded using The World Health Organization Drug Dictionary (WHODrug). Prior and concomitant medications will be tabulated by therapeutic class and generic name.

### **8.3.7 Interim Analysis**

No interim efficacy analysis is planned for the study prior to all patients completing 28 weeks of study treatment.

## **8.4 Statistical Analyses Plan**

A detailed Statistical Analysis Plan (SAP) will be finalized prior to database lock of the primary efficacy analysis of the study after all patients have completed 28 weeks of treatment or terminated before this timepoint. Any significant changes to the analyses described in this protocol will be highlighted in the SAP and the Clinical Study Report.

## 9 DIRECT ACCESS TO SOURCE DOCUMENTS

Following site prequalification and/or initiation of the study site, periodic monitoring visits and site closeout visits will be made by Sponsor or its designee. The investigator must provide direct access to, and allocate sufficient space and time for, the monitor to inspect patient source records, eCRFs, queries, collection of local laboratory normal ranges (if applicable), investigational product accountability records, and regulatory documents in accordance with Good Clinical Practices (GCP) and ICH E6 guideline.

The purpose of study monitoring is to verify the following:

- The rights and well-being of human patients are protected
- The reported data are accurate, complete, and verifiable from source documents
- All data are collected, tracked, and submitted by the site to Sponsor or designee, including unscheduled and missed assessments
- The reported data are reconciled across all data sources (e.g., laboratory, safety, interactive web response system, clinical databases)
- The conduct of the study is in compliance with the currently approved protocol/amendment(s), with GCP, and with the applicable regulatory requirement(s)

The investigator must also permit the FDA or other applicable regulatory authorities to inspect facilities and records pertaining to this study if so requested. If the investigator is notified of an inspection pertaining to this study by the FDA or other applicable regulatory authorities, the investigator must notify Sponsor immediately.

## **10 QUALITY CONTROL AND QUALITY ASSURANCE**

### **10.1 Data Quality Assurance**

The following steps will be taken to ensure that the study is conducted by the study site in compliance with the study protocol, GCP, and other applicable regulatory requirements.

- Investigator meeting and/or investigator site initiation
- Routine study site monitoring
- Documented study and system training
- Electronic case report form (eCRF) and query review against source documents

### **10.2 Audit and Inspection**

Authorized representatives of the Sponsor, a regulatory authority, an independent ethics committee (IEC) or an institutional review board (IRB) may visit the Investigative Site to perform audits or inspections, including source data verification. The Investigator will allow the Sponsor auditor, regulatory authority or ethics committee representative to inspect the drug storage area, study drug stocks, drug accountability records, patient charts and study source documents, and other records relative to study conduct. The purpose of an audit or inspection is to systematically and independently examine all study-related activities and documents to determine whether these activities were conducted, and data were recorded, analyzed, and accurately reported according to the protocol, GCP guidelines of the International Conference on Harmonisation, and any applicable regulatory requirements. The investigator should contact the Sponsor immediately if contacted by a regulatory agency about an inspection.

## **11 ETHICS**

### **11.1 Ethical Considerations**

The study will be conducted in accordance with FDA regulations, the International Conference on Harmonisation (ICH) E6 Guideline for GCP, the Declaration of Helsinki, any other applicable regulatory requirements, and Institutional Review Board (IRB) or independent ethics committee (IEC) requirements.

### **11.2 Communication with the Institutional Review Board or Independent Ethics Committee**

This protocol, the Informed Consent Form, the Investigator's Brochure, and any information to be given to the patient must be submitted to a properly constituted IRB/IEC by the investigator for review and approved by the IRB/IEC before the study is initiated and before any investigational product is shipped to the investigator. In addition, any patient recruitment materials must be approved by the IRB/IEC before the material is used for patient recruitment.

The investigator is responsible for obtaining reapproval by the IRB/IEC annually or more frequently in accordance with the regulatory requirements and policies and procedures established by the IRB/IEC. Copies of the investigator's annual report and other required report to the IRB/IEC and copies of the IRB/IEC continuance of approval must be furnished to FibroGen. A copy of the signed form FDA 1572 must also accompany the above approval letter provided to FibroGen.

Investigators are also responsible for promptly informing the IRB/IEC of any protocol changes or amendments, changes to the Investigator's Brochure, and other safety-related communications from FibroGen. Written documentation of IRB approval must be received before the amendment is implemented.

Investigators must also enter the names of the staff that are involved in the study on the Delegation of the Authority form and sign the form (including their responsibilities). This form must be updated when responsibilities of the staff change.

### **11.3 Informed Consent Form**

No study procedure may be implemented prior to obtaining a signed, written Informed Consent Form (ICF) from the patient or the patient's legally authorized representative. IRB review and approval are required for the ICFs. The final IRB/IEC approved ICFs must be provided to FibroGen for regulatory purposes.

If there are any changes to the Sample ICF(s) during the patients' participation in the study, the revised ICF(s) must receive the IRB/IEC's written approval before use and patients must be reconsented to the revised version of the ICF.

Guidance for Clinical Teams: For studies conducted in the United States, each patient must provide his or her consent for the use and disclosure of personal health information under the U.S. Health Insurance Portability and Accountability Act (HIPAA) regulations by signing a HIPAA Authorization Form. The HIPAA Authorization Form may be part of the ICF or may be a separate document. IRB review may or may not be required for the HIPAA Authorization Form according to study site policies.

## **11.4 Patient Confidentiality**

Release of research results should preserve the privacy of medical information and must be carried out in accordance with Department of Health and Human Services Standards for Privacy of Individually Identifiable Health information, 45 Code of Federal Regulations (CFR) Parts 160 and 164, and HIPAA.

Patient medical information obtained as part of this study is confidential and may only be disclosed to third parties as permitted by the Informed Consent and HIPAA Authorization Form or separate authorization to use and disclose personal health information signed by the patient, or unless permitted or required by law. The patient may request in writing that medical information be given to his/her personal physician.

## **12 DATA HANDLING AND RECORD KEEPING**

### **12.1 Source Documents**

Source documents are original documents, data, and records that are relevant to the clinical study. The investigator will prepare and maintain adequate and accurate source documents. These documents are designed to record all observations and other pertinent data for each patient enrolled in this clinical study. Source documents must be adequate to reconstruct all data entered into the electronic database and used to resolve queries.

### **12.2 Data Collection, Handling, and Verification**

All required data will be entered into an electronic database by authorized site personnel. Data will be entered into a validated, clinical database compliant with 21 CFR Part 11 regulations. The database will be a secured, password-protected system with full audit trail.

All patient data will be reviewed by Sponsor and/or designee. Data that appear inconsistent, incomplete or inaccurate will be queried for site clarification.

Medical history, adverse events and medications will be coded using industry standard dictionaries (e.g., MedDRA and WHODrug).

The investigator is responsible for reviewing, verifying, and approving all patient data (i.e., eCRFs and queries prior to study completion) and ensuring that all data is verifiable with source documents.

### **13 FINANCING AND INSURANCE**

Financing and insurance are addressed in a separate document.

## **14 PUBLICATION POLICY**

A detailed explanation of the Sponsor's publication policy is described in the Clinical Trial Agreement.

## **15 INVESTIGATOR REQUIREMENTS**

The investigator must be medically qualified to directly supervise the conduct of the study at his or her site. The investigator will permit study-related monitoring, audits, IRB/IEC review, and regulatory inspection(s), providing direct access to source data/documents.

### **15.1 Study Drug Accountability**

The investigational product (roxadustat/placebo) required for completion of this study will be provided by Sponsor. The recipient will acknowledge receipt of the drug by returning the appropriate documentation form indicating shipment content and condition. Damaged supplies will be replaced.

The investigational product, including partial and empty bottles, must be maintained at the study site until Sponsor or its designee verifies drug accountability and provides instruction for destruction or the return of the investigational product to Sponsor's drug distribution depot.

Accurate records of all study drug received, dispensed, returned, and disposed of by the study site according to the Study Reference Manual or Pharmacy Manual should be recorded using the Drug Inventory Log.

### **15.2 Disclosure of Data**

Data records generated by this study must be available for inspection upon request by representatives of the FDA or other regulatory agencies, national and local health authorities, Sponsor's monitors/representatives and collaborators, auditors, and the IRB/IEC for each study site.

The Investigators should promptly notify the Sponsor and/or designee of any audits scheduled by any regulatory authorities and promptly forward copies of any audit reports received to the Sponsor.

### **15.3 Retention of Records**

The investigator shall retain records required to be maintained under 21 CFR 312.62(c) for a period of 2 years (or longer if required by local regulations) following the date a marketing application is approved for the drug for the indication for which it is being investigated. If no application is to be filed or if the application is not approved for such indication, the investigator shall retain these records until 2 years after the investigation is discontinued and the FDA is notified.

If the investigator moves or retires, he or she should identify in writing, the designee who will be responsible for record keeping. Archived data may be retained on electronic records or similar medium provided that a back-up exists and a hard copy is obtainable if required. No records will be destroyed without the prior written consent of Sponsor.



1. Eligibility review: pre-transfusion Hb measurements will be obtained via review of source document, must be obtained within 72-hours prior to transfusion; baseline Hb level will be obtained 3 to 10 days prior to registration/randomization; GFR will be done prior to registration/randomization (see [Appendix L](#))
2. Serum erythropoietin level must be  $\leq 400$  mIU/mL at screening; during the last month of treatment a serum EPO level will be drawn just prior to the next study drug dosing; patients should be told to not take their study drug until after the study visit on that day.
3. PK: see [Appendix J](#). Levels at 1-3 and 3-5 hours after dosing at clinic on Day 1 (Week 1) as well as 4-6 hours at Week 5 and 8-10 hours at Week 21 after administration at the clinic. Two samples will be obtained 0-2 hours before dosing and 2-3 hours after dosing at Week 25; vital signs will also be taken prior to the time of the PK draw
4. ECG: no clinically significant findings per PI review at screen period
5. Patients will need to have the results from the bone marrow exam and cytogenetic analysis performed for the IPSS-R criteria. Report and slides must be available for centralized review. Bone marrow exam will be done within 4 weeks of end of treatment on all patients
6. Vital signs include BP, HR, RR, temperature. These will also be done prior to each PK sample taken. If possible, use the same device for BP measurement over the course of the study. Weight at registration/randomization will be used for determination of starting dose.
7. ECOG score: must be 0,1, or 2 at last screen visit
8. LFTs = AST, ALT, TBili, alkaline phosphatase.  $ALT > 3 \times ULN$ , OR  $AST > 3 \times (ULN)$ , OR  $TBili > 1.5 \times ULN$  will exclude a subject from entering the study (see [Appendix H](#) and [Appendix O](#) for liver monitoring information)
9. Serum chemistry = sodium, potassium, chloride, bicarbonate, BUN, creatinine, glucose, calcium, magnesium, phosphorus, LDH, albumin (Central Lab) – see [Appendix K](#)
10. Pregnancy Test: must be negative for women of child bearing capacity at screening. Additional pregnancy testing for women of child bearing capacity will also be done at Weeks 13, 25, 39, EOT and Post-EOT visits.
11. Recording of Transfusions: all RBC transfusions from 8 to 16 weeks prior to first dose throughout end of treatment. For study entry, patients are considered to have LTb if they received 1 to 4 pRBC within 8 weeks prior to registration/randomization. Patients with 1 pRBC/8weeks must have a documented history of requiring 1 pRBC/8weeks in at least 2 consecutive 8 weeks periods in the 16 weeks preceding registration/randomization. Pre and post transfusion Hb will be collected at 8 weeks post-registration/randomization. The PI and site staff will utilize their own institutional criteria for the determination of when to transfuse a patient. **Open-Label patients only**, the requirement to demonstrate transfusion dependence can also be met by a PI starting this particular patient on pRBC transfusion during the screening period.
12. CBC = Hb, HCT, mean corpuscular volume (MCV), mean corpuscular hemoglobin (MCH), mean corpuscular hemoglobin concentration (MCHC), RBC, WBC, platelets, differential; Regarding Central Lab Hb values: Two Hb values are obtained at Screening Visit 1 and 2, only 1 of 2 value needs to meet the  $Hb \leq 10.0$  g/dL criteria.
13. Iron biomarkers = serum iron, ferritin, TIBC, TSAT, and UIBC.
14. Registration into the OL component or Randomization into the DB component to occur on Day 1, Week 1 prior to first dose which should be given at the site
15. HRQoL questionnaires include PROMIS and EQ-5D-5L. ONLY for patients randomized to DB study
16. Study drug dosing: begins on the first day of dosing (Day 1/Week 1). All study procedures must be completed prior to administration of the 1st dose of study treatment. Dosing should occur at approximately the same time of day. Roxadustat/placebo (study medication) can be taken with water with or without food. The dose of statins should not exceed the protocol-recommended daily dose in the protocol.
17. Last dose of study drug must be prior to EOT assessments
18. Dose adjustment review every 8 weeks for upward adjustments. Week 9 evaluation requires determination of Erythroid Response. A re-assessment will be done for these patients at Week 12 and if TI is observed the dose will not be increased.
19. Must be at least 28 days post-dose/EOT

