### 6.3.1 Study Procedures and Assessments by Visit

#### 6.3.1.1 Study Procedures and Assessments to be Done at All Study Visits

The following will be done at ALL study visits within the Treatment and Follow-Up Periods:

- Recording of transfusions
- Central CBC with Hb level and WBC differential
- Local hemoglobin level (hemocue device is encouraged but not required)
- Review and record AEs
- Review and record concomitant medications, procedures and non-drug therapies
- Review hemoglobin level for any dose adjustments that are deemed necessary ([Appendix C](#) and [Appendix D](#))
- Ensure patient dosing compliance

Local laboratory testing of Hb for dose adjustment decisions will be done at the Local level – use of the Hemocue device is encouraged but not required. Central laboratory values of Hb will be used for all data analysis purposes

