**Appendix B - Patients who Discontinue Study Medication Prior to Week 52**

Procedures	EOT 	Post - EOT 	Every 8 weeks assessment from Post-EOT WK 4 visit. Last visit at Week 52 from first dose.	
		WK 4	WK 12	→
Informed consent signature				
Eligibility Review 				
Med History/ Demographics				
Physical Exam	X	X		
Weight 				
HbsAg, anti-HCV AB, HIV				
Endogenous serum EPO Level 	X	X	X	
B12, Folate	X	X		
PK 				
ECG 	X	X		
Bone marrow aspirate and biopsy 	X			
Vital signs 	X	X	X	
ECOG Score 	X	X		
Serum Lipid Panel	X	X		
LFTs 	X	X	X	
Serum chemistry 	X	X	X	
PT, PTT	X	X		
Hepcidin	X	X	X	
Pregnancy test 	X	X		
C-reactive protein	X	X		
Recording of transfusions 	→			
CBC 	X	X	X	
Local Hemoglobin	X	X	X	
Reticulocyte count; CHr	X	X		
Iron Biomarkers 	X	X	X	
Registration/Randomization to the study				
HRQoL Questionnaires 	X	X		
Study drug dosing				
Study drug dispensation				
Dose adjustment review				
AEs/Con Meds/Procedures	→			

For footnotes please refer to [Appendix A](#)

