Week 28 visit: Week 28 visit should be conducted at the end of 28 weeks of treatment (2 weeks after Week 27 Visit). Primary analysis of efficacy will be conducted when all the randomized (DB) patients complete 28 weeks of treatment or are discontinued from study medication before this time. **End-of-Treatment (EOT/ET) Visit:** Patients who complete 52-week treatment period or discontinue study medication early (Early Termination before week 52) will have an EOT/ET visit.

Post-Treatment Follow-Up Period: Week 56 (Post-EOT Week 4)

Post-Treatment Follow-Up Period for ET Patients: Patients who discontinue early will have visits every 8 weeks until Week 52.

End of Study (EOS) Visit: All patients who complete 52 weeks (of treatment with study medication) will undergo a 4 week follow-up period after the last dose of study medication and will return for the End of Study (EOS) visit. Patients who discontinue study medication early (for any reason) will remain in the study through the entire 52 week study period. Patients will have a 4 week follow-up visit after stopping study medication/ET visit and then be followed up at a reduced visit schedule of every 8 weeks until the end of the study.

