12.3. Analysis of Double-Blind Efficacy Endpoints

12.3.1. Analysis of Primary Efficacy Endpoint

The primary efficacy endpoint for this study is proportion of patients who achieved TI ≥ 56 consecutive days (e.g., 8 weeks) since first dose in the first 28-week of treatment. TI is defined as the absence of any intravenous RBC transfusion (packed cell or whole blood) during any consecutive 56 days during the treatment period (e.g., Days 1 to 56, Days 2 to 57, Days 3 to 58). All RBC transfusions from 8 to 16 weeks prior to first dose until end of study will be recorded on CRF. TI will be estimated in the duration beginning with the first dose date (Day 1) and ending with the date of end of treatment or last visit date at

week 28, whichever comes earlier. RBC transfusions after end of treatment will be recorded on the CRF until the last visit at week 52 from first dose but will not be used to define TI.

The endpoint will be also analyzed for the end of the 52-week study treatment period as a secondary endpoint.

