12.3.3. Analysis of Secondary Efficacy Endpoints

All secondary endpoints measured for treatment periods will be analyzed both for the first 28 weeks of treatment and for 52-week study treatment period. Others will be analyzed for the time during the study. The secondary efficacy endpoints will be analyzed based on the FAS population unless it is specified otherwise. Analyses using the PPS will be used as sensitivity analyses.

12.3.3.1. Proportion of Patients who achieved TI ≥ 56 consecutive days anytime during the study

The proportion of patients who achieved TI for ≥ 56 consecutive days will be summarized using the FAS and PPS and will be compared between the two treatment groups. TI is defined as the absence of any intravenous RBC transfusion (packed cell or whole blood) during any consecutive 56 days anytime during the study. TI will be estimated in the duration beginning with the first dose date (Day 1) and ending with the end of study or treatment discontinuation due to AE/SAE or death, whichever comes earlier. RBC transfusions after end of treatment will be recorded on CRF until the last visit at week 52 from first dose and will be used to define TI.

The p-value obtained will be reported for the test of the null hypothesis that there is no difference between the two treatment groups.

Similar methods will be used as for the primary endpoint.

This analysis will take into account the potential intercurrent events as follows:

1. Treatment discontinuation due to any reasons: using Treatment-policy strategy: regardless of these intercurrent events occurred; the TI will be estimated using RBC transfusion records in the whole study duration.
2. Death: using Treatment-policy strategy: regardless of these intercurrent events occurred; Patients who died prior to week 8 will be classified as non-responders. TI will be estimated using RBC transfusion records for the study duration up to death.

12.3.3.2. Proportion of Patients Who Achieved $\geq 50\%$ Reduction in Number of pRBC Transfusions over 8 Weeks Compared to Their Baseline for Any 8 Week Period during the Study (Factor of Erythroid Response)

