The proportion of patients who achieved TI for ≥ 20 Weeks (140 Days) will be summarized using the FAS and PPS and will be compared between the two treatment groups. TI is defined as the absence of any intravenous RBC transfusion (packed cell or whole blood) during any consecutive 140 days anytime during the study. TI will be estimated in the duration beginning with the first dose date (Day 1) and ending with the end of study or treatment discontinuation due to AE/SAE or death, whichever comes earlier. RBC transfusions after end of treatment will be recorded on CRF until the last visit at week 52 from first dose and will be used to define TI.

The p-value obtained will be reported for the test of the null hypothesis that there is no difference between the two treatment groups.

Similar methods will be used as in [Section 12.3.3.1](#). Similar strategies will be implemented for potential intercurrent events.

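### Protocol Appendix A footnote 11 stops transfusion recording at end of treatment, but gatekept Tests 3, 4 and 7 need post-treatment records and the SAP has no rule for days without them

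*Protocol*

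**What the plan says.** The documents give several end points for recording transfusions.

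- **Protocol Appendix A, footnote 11:** "Recording of Transfusions: all RBC transfusions from 8 to 16 weeks prior to first dose throughout end of treatment". The row for recording transfusions in Appendix B carries the same footnote. Appendix B applies only to patients who stop study drug before Week 52.
- **Protocol Appendix B, the row itself:** an arrow that continues past the end-of-treatment visit, over a schedule headed "Every 8 weeks assessment from Post-EOT WK 4 visit. Last visit at Week 52 from first dose".
- **Protocol 6.3.1.1:** "The following will be done at ALL study visits within the Treatment and Follow-Up Periods". The first item on the list that follows is the recording of transfusions.
- **SAP 12.3.1:** "All RBC transfusions from 8 to 16 weeks prior to first dose until end of study will be recorded on CRF". Later in the same paragraph, recording after treatment is said to run only to the last visit at Week 52.
- **SAP 12.3.3.1 and 12.3.3.5:** "RBC transfusions after end of treatment will be recorded on CRF until the last visit at week 52 from first dose", adding that these records are used to define transfusion independence (TI).

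The scored window for Test 3 (TI of at least 56 days at any time, SAP 12.3.3.1), Test 4 (at least 50% reduction in transfusions, SAP 12.3.3.2) and Test 7 (TI of at least 140 days, SAP 12.3.3.5) starts at first dose, "ending with the end of study or treatment discontinuation due to AE/SAE or death, whichever comes earlier". SAP 3.1 has early discontinuers seen until Week 52. Patients who complete 52 weeks have a further 4 weeks of follow-up, after which they "will return for the End of Study (EOS) visit".

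**The concern.** TI is defined by the absence of transfusion over a run of days. In the data, a day on which nobody asked about transfusions looks the same as a day without one. SAP 5.4 allows no substitution for missing data unless the SAP specifies it, and I found no rule in the SAP for days without transfusion ascertainment.

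The exposed patients are those who stop for reasons other than an adverse event. Protocol 4.3 lists lack of efficacy and patient decision among the reasons for stopping. These patients remain in the scored window after stopping. If their later transfusions are not recorded, a treatment failure can be counted as a responder.

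Test 3 is third of ten in the fixed sequence of SAP Table 4. A distorted result there also decides whether Tests 4 to 10 can be tested.

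**Working it through.** The plan states no figure on this point, so the check compares recorded days with scored days.

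**Inputs**
- The SAP visit-window tables (19.3.1) schedule Week 52 at Day 7 × 52 + 1 = Day 365.
- End of study is therefore Day 365 for early discontinuers. For completers, SAP 3.1 puts it 4 weeks after the last dose, about Day 365 + 28 = Day 393.
- Run lengths are 56 days (Tests 3 and 4) and 140 days (Test 7).
- Scoring stops at discontinuation for an AE or SAE, per the window sentence of each section. The intercurrent-event paragraph of SAP 12.3.3.1 instead speaks of discontinuation for any reason. I follow the window sentence.

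**Scored but unrecorded days under each reading**

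| Recording rule | Early non-AE discontinuer, end of treatment on Day e | 52-week completer |
|---|---|---|
| Footnote 11 alone | 365 − e | about 28 |
| SAP Week 52 sentence alone | 0 | up to 393 − 365 = 28 |
| Protocol 6.3.1.1, or the SAP's end-of-study sentence | 0 | 0 |

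**Early discontinuers under footnote 11.** The unrecorded tail alone reaches the required length when:
- 365 − e ≥ 56, so e ≤ 309 (about Week 44), for Tests 3 and 4. For Test 4, 56 days with no recorded transfusion score as a 100% reduction.
- 365 − e ≥ 140, so e ≤ 225 (about Week 32), for Test 7.

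A shorter tail can still complete a run that began on treatment, so these days mark where the tail suffices by itself.

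**Completers under the Week 52 sentence.** A 28-day tail cannot make a qualifying run alone.
- Test 3: it changes the result only if the patient is 28 to 55 days transfusion-free at Week 52 (56 − 28 = 28; at 56 the patient already qualifies).
- Test 7: the corresponding range is 112 to 139 days.
- Test 4: the tail fills at most 28/56, or half, of an 8-week window.

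**Tests 1 and 2.** Both use on-treatment windows, so every reading records all their scored days.

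**The case against.** The strongest reply is that the plan clearly intends post-treatment recording. Protocol 6.3.1.1, the Appendix B arrow and three SAP sections require it, and a single footnote does not. The SAP also defines TI by the absence of any transfusion, not by the absence of a recorded one. This stands: false responders arise only where the footnote is followed over those passages, or where follow-up lapses.

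Two further points also stand. First, the SAP is written for Amendment 03 (30 January 2020), while the protocol supplied is Amendment 02. SAP 12.3.1 uses the footnote's look-back wording but ends at end of study, so the footnote may already have been changed. Second, the Week 52 sentence fits early discontinuers, whose last visit is Week 52; for them recording and scoring end together.

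A reader might infer three stronger things that the documents do not support.
- **That unrecorded days will count as TI.** This depends on site behaviour that most of the text contradicts.
- **That completers' last 28 days are scored but not recorded.** SAP 12.3.1 also says recording runs to end of study. That is an unresolved inconsistency, not an established gap.
- **That the treatment difference shrinks enough to stop the testing sequence.** Take the SAP's planning rates of 56% and 13%, and assume a fraction x of each arm stops for non-AE reasons by Day 309, independently of response, with every such site following the footnote. The rates become 0.56 + 0.44x and 0.13 + 0.87x. For x = 10%, 20% and 30% the difference falls from 43 points to 38.7, 34.4 and 30.1. Those planning rates belong to the 28-week primary endpoint and the stop fractions are invented. Even so, with the 140 enrolled patients split 84:56, exact two-sided Fisher power is 99.6%, 97.7% and 92.7% (the planned test is a stratified CMH).

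**Conclusion.** The contradiction is real and should be corrected. Footnote 11 conflicts with the protocol body, with the Appendix B row it annotates and with the SAP. It does so for the patients whose post-treatment records Tests 3, 4 and 7 depend on. Where it is followed, the unrecorded tail for a non-AE discontinuer is at least 56 days for a stop by Day 309 and at least 140 days for a stop by Day 225. Separately, the SAP's two recording end points leave up to about 28 days unclear for completers.

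These day counts rest on Week 52 falling on Day 365 and on the window sentences in SAP 12.3.3. The documents do not say how many patients stop for non-AE reasons, when, in which arm, or which instruction sites follow, so neither the size nor the direction of any bias can be established. If such stops were equally common in both arms, the difference would shrink, because placebo has more non-responders to convert. If they were unequal, the arm with more of them would gain more. This is an inconsistency to reconcile, not a demonstrated bias, and the primary endpoint is not touched.

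**What to change.** 1. Check whether Amendment 03 already changed footnote 11. If not, change it to require recording of all RBC transfusions through the last study visit for every patient, in line with Protocol 6.3.1.1 and the Appendix B arrow.
2. In SAP 12.3.1, 12.3.3.1 and 12.3.3.5, use end of study as the single recording end point.
3. In SAP 12.3.3.1, 12.3.3.2 and 12.3.3.5, close the scored window at the earlier of its present end and the last date on which the patient's transfusion history was reviewed. Days after the last review then cannot be scored as transfusion-free.

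A fixed cap on scoring at Week 52 is not needed. It would discard completer follow-up that item 1 asks sites to record, and it would alter the estimand of response at any time during the study.

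The cost is one footnote and a few SAP sentences. The downside is that some patients with lapsed follow-up may change from responder to non-responder in Tests 3, 4 and 7.
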